6.9.1.1. Important Potential Risks and Adverse Events of Special Interest (AESI)

Vector-induced hepatic effects (e.g., increased aminotransferase levels) following IP administration and infusion-related reactions (IRR) including hypersensitivity during or following IP administration have been identified as important potential risks and adverse events of special interest (AESIs) for DTX401. Since subjects are enrolled in Study 401GSDIA02 at 52 weeks after IP infusion in Study 401GSDIA01, it is not expected that any IRRs will be observed in Study 401GSDIA02 and will be considered as not applicable for this study.

MedDRA search strategy to identify PTs for vector-induced hepatic effects is included in [Appendix 2](#). Subject Incidence of TEAEs of vector-induced hepatic effects will be tabulated by SOC and PT.

6.9.1.2. Potential Risks and Adverse Events of Special Interest

Adrenal insufficiency is considered a potential risk of study-related procedures associated with use of corticosteroids and is an AESI. Since subjects are enrolled in Study 401GSDIA02 at 52 weeks after IP infusion in Study 401GSDIA01, it is not expected that corticosteroids will be administered in 401GSDIA02 study to minimize or prevent potential vector-induced hepatic events (eg, transaminase elevations). However, in the event elevated ALT or AST is observed in 401GSDIA02 study due to the AAV8 vector and corticosteroids are required (and is not due to underlying disease), subject incidence of TEAEs of adrenal insufficiency will be tabulated by SOC and PT. MedDRA search strategy to identify PTs for these events is included in [Appendix 2](#).

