6. STATISTICAL ANALYSIS

6.1. General Principles

All analyses in the study will be descriptive; no formal hypotheses will be tested. An integrated analysis using data from both Study 401GSDIA01 and Study 401GSDIA02 will be performed to summarize and assess the long-term safety and efficacy of DTX401; there will not be a standalone analysis of data from only Study 401GSDIA02.

Continuous variables will be summarized by number of subjects, mean, SD, standard error (SE), median, Q1, Q3, minimum, and maximum values. Categorical variables will be summarized by number and percentage of subjects. All summary tables will be presented by scheduled study visit and no analysis windows will be used, unless specified otherwise. Study visits from both studies 401GSDIA01 and 401GSDIA02 will be included in summary tables.

All summary tables will be presented by dose cohort of DTX401 (see below), Cohorts 2, 3, 4 combined (i.e., cohorts for dose 2 combined), and overall, unless specified otherwise.

The dosing cohorts are:

- Cohort 1: Dose 1 (2.0×10^{12} GC/kg) with a reactive steroid regimen (prednisone starting dose of 40 mg/day)
- Cohort 2: Dose 2 (6.0×10^{12} GC/kg) with a reactive steroid regimen (prednisone starting dose of 40 mg/day)
- Cohort 3: Dose 2 (6.0×10^{12} GC/kg) with an optimized reactive steroid regimen (prednisone starting dose of 60 mg/day)
- Cohort 4: Dose 2 (6.0×10^{12} GC/kg) with a prophylactic steroid regimen

SAS[®] software version 9.4 or higher will be used to perform statistical analyses unless otherwise specified.

Handling of missing or incomplete data is described in [Appendix 1](#).

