6.9.1. Adverse Events

Adverse events will be coded by system organ class (SOC) and preferred term (PT) using the current version of Medical Dictionary for Regulatory Activities.

An AE (classified by preferred term) will be considered a treatment emergent adverse event (TEAE) if it occurred on or after the first dose of IP.

AEs from both studies 401GSDIA01 and 401GSDIA02 will be combined for this analysis. Further, AEs from Study 401GSDIA02 will also be summarized separately.

Subject incidence of TEAEs will be tabulated as the follows. The number of events will also be included.:

- Summary of TEAEs
- TEAEs by SOC and PT
- Related TEAEs by SOC and PT

- Serious Related TEAEs by SOC and PT
- Grade 3 or 4 TEAEs by SOC and PT
- Fatal TEAEs by SOC and PT
- TEAEs leading to discontinuation of study by SOC and PT
- TEAEs by PT
- TEAEs by PT and greatest severity
- TEAEs by their time of occurrence (<1, 1-2, 2-3, 3-4, 4-5, 5-6 years since the IP administration)

The severity will be based on the most current version of CTCAE. If an AE cannot be graded based on CTCAE, the investigator will assign a severity based on 1 = mild, 2 = moderate, 3 = severe, 4 = life threatening, and 5 = death. Detailed listings for all AEs, serious TEAEs, TEAEs leading to the discontinuation of study, and death will also be generated.

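### The adrenal insufficiency AESI table depends on new steroid use in the follow-up study, although the adverse-event analysis pools both studies from dosing

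*SAP*

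**What the plan says.** **Scope of the adverse-event analysis.** SAP 6.1 sets an integrated analysis of both studies and adds that "there will not be a standalone analysis of data from only Study 401GSDIA02". SAP 6.9.1 applies this to adverse events: "AEs from both studies 401GSDIA01 and 401GSDIA02 will be combined for this analysis". It then adds a second summary: "Further, AEs from Study 401GSDIA02 will also be summarized separately". An event "will be considered a treatment emergent adverse event (TEAE) if it occurred on or after the first dose of IP", so the window opens at dosing in Study 401GSDIA01. One planned table splits events by onset: "TEAEs by their time of occurrence (<1, 1-2, 2-3, 3-4, 4-5, 5-6 years since the IP administration".

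**Adrenal insufficiency.** SAP 6.9.1.2 states: "Adrenal insufficiency is considered a potential risk of study-related procedures associated with use of corticosteroids and is an AESI". It reasons that subjects enter 52 weeks after the infusion, so corticosteroids are not expected in Study 401GSDIA02. The commitment to a table by system organ class (SOC) and preferred term then follows a condition: "However, in the event elevated ALT or AST is observed in 401GSDIA02 study due to the AAV8 vector and corticosteroids are required". A parenthesis adds that underlying disease must not be the cause. Appendix 2 lists the adrenal search terms.

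**Infusion-related reactions.** SAP 6.9.1.1 names these an AESI too, but says "it is not expected that any IRRs will be observed in Study 401GSDIA02 and will be considered as not applicable for this study". Appendix 2 has no search terms for them.

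**Other risks.** Hepatic effects (6.9.1.1), dorsal root ganglion and peripheral nerve effects (6.9.1.3) and gene therapy class effects (6.9.1.4) are tabulated without a condition.

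**Exposure.** Protocol 5.4 lists four cohorts in Study 401GSDIA01, all with a reactive or prophylactic steroid regimen. Protocol 7.1.3.6 says DTX401 was given only in that study.

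**The concern.** The two AESI rules argue from what is expected in Study 401GSDIA02 alone, yet they sit inside an analysis that starts a year earlier. The SAP ties adrenal insufficiency to corticosteroid use, and the planned steroid regimens belong to the parent study. The period of most interest for this AESI is therefore in the combined data but has no assured AESI table.

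The trigger also has nothing to do with whether an adrenal event occurred. It turns on liver enzymes, their attribution to the vector and a need for steroids during follow-up. At stake is whether a reader of the long-term safety report can see directly how many subjects had the AESI.

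**Working it through.** The plan gives no figure to reproduce: the study is descriptive and its size has no power basis. The check is a comparison of passages, with simple proportions for scale.

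**1. Period covered.** By SAP 6.9.1, treatment-emergent events run from the dose onward, from both studies, with a first onset category of under 1 year. Year 1 is in scope.

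**2. Exposure.** The infusion and the planned prednisone regimens lie in Study 401GSDIA01 (Protocol 5.4 and 7.1.3.6). The SAP uses year-1 steroid data elsewhere: 6.9.3 plots ALT and AST with prednisone dose over time, and 6.9.8 plots ELISPOT response with ALT and steroid use, from both studies.

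**3. The trigger, case by case.**

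| Situation | Adrenal event in combined data? | Table required by SAP 6.9.1.2? |
|---|---|---|
| Event in year 1, no new steroids in 401GSDIA02 (the expected steroid case) | Yes | No |
| Event in 401GSDIA02 after parent-study steroids, no new steroids | Yes | No |
| Event in 401GSDIA02 after steroids given for a reason other than a vector-related ALT/AST elevation | Yes | No |
| No adrenal event; one subject has a vector-related elevation needing steroids in 401GSDIA02 | No | Yes, empty |
| Year-1 event in one subject; a different subject meets the trigger later | Yes | Yes; by the SAP 6.9.1 definition it includes the year-1 event |

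Comparing the first and last rows, the same year-1 event is grouped or not according to what happens to someone else.

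The second row is a possibility the plan can detect. Protocol Table 1 schedules cortisol and ACTH around the fasting challenges, SAP 6.8.1 flags end-of-challenge cortisol below 10 µg/dL, and low cortisol is among the Appendix 2 adrenal terms. Nothing in the documents says such an event has occurred.

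**4. What remains without the AESI table.** All preferred terms still appear with subject incidence and event counts in the SAP 6.9.1 tables, and all adverse events are listed. Only the grouping is absent.

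**5. Scale.** Appendix 2 lists 13 adrenal terms, mixing diagnoses with laboratory findings. Assume all 12 parent-study subjects enrolled, 3 per cohort:

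- One subject is 1/3 = 33.3% of a cohort, 1/9 = 11.1% of Cohorts 2-4 combined, and 1/12 = 8.3% overall.
- Preferred-term rows cannot be added, because one subject may be in several. Two adrenal rows of one subject each (hypothetical) fit a grouped incidence anywhere from 1/12 = 8.3% to 2/12 = 16.7%.
- An SOC row counts subjects with any event in that class, adrenal or not. It equals the AESI count only if all the adrenal terms reported share a class and no other event adds a subject.

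**The case against.** The strongest reply is that nothing goes missing. Every adrenal event or infusion reaction since dosing is in the general tables and the listings, and follow-up events are also in the separate 401GSDIA02 summary. Protocol 12.4.1 promises subject counts by SOC as well as by preferred term. With about 12 subjects, a reader with the listings can regroup the events by hand. All of this stands, and it limits the point to presentation of the AESI.

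The planned AESI tables are themselves described only as by SOC and preferred term. Whether they carry an any-event row is left to the separate shell document (SAP 8). That also stands, so the fix has to ask for the row explicitly.

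On infusion reactions, the SAP explains its exclusion: no product is given in this study and entry is 52 weeks after a single infusion. The parent study has its own report, which may cover them. This half is therefore weaker. But SAP 6.5 to 6.7 defer explicitly to that report for demographics, medical history and medications, while the AESI sections do not.

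The Protocol synopsis says the 401GSDIA02 safety database holds results from that study only. That describes a database; the same synopsis and SAP 6.9.1 specify pooled analysis. A follow-up-only rationale would suit the separate 401GSDIA02 summary, but neither AESI section confines itself to it.

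Finally, a reactive regimen does not show how many subjects took steroids or for how long, so the size of the group at risk is unknown.

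**Conclusion.** The inconsistency is real and the adrenal condition should go. In the expected case, a named AESI with its own 13-term search list gets no grouped subject incidence in the integrated analysis, by a rule unrelated to whether events occurred. The infusion-reaction statement needs a narrower scope or a pointer to the parent report.

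Stronger readings are tempting but unsupported. A reader might infer that adrenal events or infusion reactions drop out of the report, or that no incidence would be shown; the general tables and listings rule that out. A reader might also size the loss with an example, such as three subjects with three different terms showing as three rows of 1/12 = 8.3% and no 3/12 = 25% total. That is hypothetical: the documents report no adrenal event count, and SOC-level counts could show part of the total. Nor do the documents show that the parent-study report omits these AESIs.

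The verdict rests on reading the condition as the only commitment to an adrenal table, and on SAP 6.9.1's dosing-onward definition applying to its subsections. The percentages assume that all 12 subjects enrolled.

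**What to change.** 1. In SAP 6.9.1.2, delete the condition. Tabulate subject incidence of treatment-emergent adrenal insufficiency on the combined data, using the Appendix 2 terms, with an any-event row above the SOC and preferred-term rows. Present it by cohort, Cohorts 2-4 combined and overall, alongside the hepatic-effects table.
2. In SAP 6.9.1.1, limit the not-applicable statement on infusion-related reactions to the separate 401GSDIA02 summary. For the combined analysis, either tabulate them and add search terms to Appendix 2, or state that the 401GSDIA01 report covers them.

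The cost is one extra table, or two if infusion reactions are tabulated, from adverse-event data already being combined. The infusion-reaction search terms would have to be supplied, since these documents do not contain them. No new data collection is needed.

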6.9.1.4. AAV Gene Therapy Class Effects

AAV gene therapy class effects include malignancies (new or worsening of pre-existing malignancies) and thrombotic microangiopathy. The MedDRA search strategies to identify PTs for these events is included in [Appendix 2](#). Subject Incidence of TEAEs for AAV gene therapy class effects will be tabulated by SOC and PT.

6.9.2. Physical Examination

Physical examination findings in Study 401GSDIA02 will be listed by study visit. Physical examination findings that are clinically significant per study investigator are documented and summarized as AEs.

6.9.3. Clinical Laboratory Assessments

Clinical laboratory assessments are mainly collected at central laboratory, except for data collected during CFC which is collected at local laboratory and analyzed as described in [Section 6.8.1](#). In some cases, subjects may complete safety labs (i.e., chemistry, hematology, etc.) at a local laboratory instead of at scheduled visit at a site or a home healthcare visit. That data will be mapped to appropriate scheduled visits if they are collected within +/- 14 days window from the scheduled visit date.

For all central clinical laboratory parameters ([Table 2](#)) with continuous results, absolute values and changes from baseline will be summarized by study visit. For central laboratory parameters with categorical results, results will be included in a listing because these parameters are non-critical for analysis (e.g., Urinalysis blood (by dipstick), or microscopic examination parameters, etc.). Data from both studies 401GSDIA01 and 401GSDIA02 will be included in this analysis.

Quantitative laboratory measurements reported as “< X”, i.e., below the lower limit of quantification will be converted to X/2 for the purpose of quantitative summaries, but will be presented as recorded, i.e., as “< X” in the listings. Quantitative laboratory measurements reported as “> X”, i.e., above the upper limit of quantification, will be converted to X for the purpose of quantitative summaries, but will be presented as recorded, i.e., as “> X” in the listings. In the event of repeat laboratory assessments, the last non missing value will be used.

Severity of selected chemistry and hematology laboratory parameters will be graded according to the version 5.0 of CTCAE ([Appendix 8](#)) where severity grading criteria are available. Shift tables using CTCAE grades to compare baseline to the worst post-baseline value will be produced for hematology and chemistry laboratory parameters. For some specific parameters with CTCAE grading in both high and low direction (e.g., glucose, potassium, sodium), CTCAE grades in high and low directions will be presented separately, i.e., hyper for higher values of concern and hypo for lower values of concern. Values from post-baseline unscheduled visits will also be considered when the worst post-baseline value is derived.

Listings of laboratory parameters will be provided. Individual patient profile of triglyceride with daily cornstarch intake over time will be plotted. Individual patient profile of ALT, AST, and prednisone/prednisolone dose over time will be plotted. Listings of selected laboratory parameters will be provided for subjects satisfying Hy’s law criteria (if any). Any abnormal laboratory test results which are considered as clinically significant in the medical and scientific judgment of the Investigator, are to be recorded as AEs or SAEs.

Table 2: Central Clinical Laboratory Parameters

Clinical chemistry	Lipid panel, uric acid, sodium, potassium, chloride, carbon dioxide, blood urea nitrogen, creatinine, glucose, calcium, phosphate, magnesium, albumin, total protein, creatine kinase, bilirubin (total, direct, and indirect), ALT, AST, ALP, gamma-glutamyl transferase, and lactate dehydrogenase
Hematology	Complete blood count with differential
Urinalysis	Specific gravity, pH, glucose, protein, blood (by dipstick), ketones (by dipstick), and microscopic examination (if blood or protein is found)
Coagulation panel	PT/INR, aPTT
24-Hour urine	Total protein, microalbumin, and creatinine

Abbreviations ALP = alkaline phosphatase; ALT = alanine aminotransferase; aPTT = activated partial thromboplastin time; AST = aspartate aminotransferase; PT/INR = prothrombin time/international normalized ratio.

6.9.4. Vital Signs

Vital sign measurements (heart rate in beats per minute, blood pressure [seated systolic and diastolic] in millimeters of mercury (mm Hg), and respiratory rate in millimeters of mercury (mm Hg)), and changes from baseline values will be summarized by study visit. Data from both studies 401GSDIA01 and 401GSDIA02 will be included in this analysis.

Vital sign values will be considered clinically significant if they meet both the observed-value criteria and the change-from-baseline criteria listed in [Table 3](#). The number and percentage of subjects with clinically significant post-baseline values will be tabulated. The percentages will be calculated relative to the number of subjects with available baseline values and at least 1 post-baseline assessment. The numerator will be the total number of subjects with available baseline values and at least 1 clinically significant post-baseline value.

Table 3: Criteria for Clinically Significant Vital Signs

Parameter	Flag	Criteria	
		Observed Value	Change from Baseline
Systolic blood pressure, mm Hg	High	≥ 180	Increase of ≥ 20
	Low	≤ 90	Decrease of ≥ 20
Diastolic blood pressure, mm Hg	High	≥ 105	Increase of ≥ 15
	Low	≤ 50	Decrease of ≥ 15
Pulse rate, bpm	High	≥ 120	Increase of ≥ 15
	Low	≤ 60	Decrease of ≥ 15

Weight, and BMI will be summarized by visit. Summary may be provided at last study visit as if deemed appropriate. BMI at a visit will be calculated using weight at that visit and height at screening visit in Study 401GSDIA01. Individual subject listing of vital signs will be provided. If a clinically significant change or abnormal vital sign measurement is observed per study investigator, it should be recorded as an AE or SAE.

6.9.5. Electrocardiogram

A listing of ECG results at Visit 1 (Week 52) in Study 401GSDIA02 will be provided. A single 12-lead ECG will be obtained using an ECG machine that automatically calculates the heart rate and measures PR, QRS, QT, and corrected QT intervals.

6.9.6. Symptomatic Hypoglycemic Events

The number of subjects reporting symptomatic hypoglycemic events as captured in eCRF and number of events will be summarized by visit. Data from both studies 401GSDIA01 and 401GSDIA02 will be included in this analysis.

Details of the symptomatic hypoglycemic events will be provided in a listing.

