| Version 1.0 | 30 Jan 2019 | Original Protocol |
| Version 2.0 (Amendment 1) | 17 Feb 2020 | 
An overview of changes includes the following:
 
 • Assessments for vector shedding was added only for subjects that did not demonstrated clearance in Study 401GSDIA01 (Section 11.3.11, Table 1, and Table 2) • Section 6.2.3 was updated to reflect the number of ongoing studies with DTX401 as of December 2019 • A complete physical examination was added to the Week 260 (or end of study) and Early withdrawal visit (Table 1 and Figure 2) • The recommended target carbohydrate range of the prefasting challenge dinner meal was decreased from 20-30 g to 15-20 g, and the prefasting challenge cornstarch dose was decreased from 35 g to 5 g, to minimize a potential insulin spike that could result in abrupt hypoglycemia and to normalize baseline glucose levels (Section 11.4.1 and Table 1) • Blood sample collection for measurement of glucose and lactate levels was added at the beginning of the controlled fasting challenge to provide baseline levels (Sections 11.3.7.1 and 11.4.1, and Table 1) • Instructions for glucose and lactate samples collected during the fasting challenge were corrected to state that samples should be prepared and transported in accordance with the site's standard procedures (Sections 11.3.7.1 and 11.4.1, and Table 1) • Continuous glucose monitoring was added to collect supplemental information on glucose level trends throughout the study (Sections 11.4.2 and 13.5.3, and Table 1) • The exploratory study objective and endpoint related to morning glucose level were modified to glucose level due to the addition of continuous glucose monitoring (Sections 7, 13.5.4, and 13.1.3, and Figure 2) • Collection of blood for measurement of lipid levels was added on the morning of hospital admission for the fasting challenge (Section 11.4.1 and Table 1) • Collection of blood for measurement of cortisol, fatty acid, glucagon, insulin, and ketone levels was added at the beginning and end of the fasting challenge, or more frequently at the Investigator's discretion (Sections 11.3.7.2 and 11.4.1, and Table 1) • Details regarding the collection of morning glucose levels were clarified, including instances in which a subject is unable to use the assigned continuous glucose monitor (Section 11.4.2 and Table 1) • An enzyme-linked immunospot (ELISPOT) assay was added to assess any long-term potential cell-mediated immune responses to DTX401 (Sections 8.1, 11.3, 11.3.9.1, 13.6, Figure 2, and Table 1) • Text was added to clarify that the reporting period for hypoglycemic events is throughout the study (Sections 11.3.6 and 13.4.2) • The table of Clinical Laboratory Parameters was updated for completeness (Table 2) |

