| Targeted physical examination ¹¹ | | X | X ⁷ | X | X ⁷ | (X) | X ⁷ | (X) | X ⁷ | (X) | X ^{7,10} | X ^{7,10} | | | |
| 12-Lead ECG | X ⁷ | | | | | | | | | | | | | | |
| Liver MRI ¹² | X | | | | | | | | | | X | | | X | |
| Liver ultrasound | | | X ⁷ | | X ⁷ | | X ⁷ | | X ⁷ | | X ⁷ | | X ⁷ | | |
| AE/SAE monitoring | X ⁷ | X | X ⁷ | X | X ⁷ | X | X ⁷ | X | X ⁷ | X | X ⁷ | X | X | X ⁷ | |
| Assessment of symptomatic hypoglycemic events | X ⁷ | X | X ⁷ | X | X ⁷ | X | X ⁷ | X | X ⁷ | X | X ⁷ | X | X ⁷ | X ⁷ | |
| Assessment of prescribed diet and dietary intake ¹³ | X ⁷ | X | X ⁷ | X | X ⁷ | X | X ⁷ | X | X ⁷ | X | X ⁷ | X | X ⁷ | X ⁷ | |
| Assessment of cornstarch (or equivalent) use ¹³ | X ⁷ | X | X ⁷ | X | X ⁷ | X | X ⁷ | X | X ⁷ | X | X ⁷ | X | X ⁷ | X ⁷ | |
| CGM ¹⁴ | X | X | X | X | X | X | X | X | X | X | X | X | X | X | |

| Procedure | Period | – | Follow-up: Year 2 ¹ | | | | Follow-up: Years 3-6 ² | | | | | | | | Early Withdrawal |
|---------------------------------------------------------------------------------------------|---------------------|--------------------------------|--------------------------------|---------|--------------------|----------|-----------------------------------|----------|--------------------|----------|--------------------|----------|-----------------------|-----------------------|------------------|
| | Week | Visit 1 (Week 52) ³ | Week 65 | Week 78 | Week 91 | Week 104 | Week 130 | Week 156 | Week 182 | Week 208 | Week 234 | Week 260 | Week 286 ⁴ | Week 312 ⁴ | |
| | Visit Window (Days) | ±7 | ±14 | ±14 | ±14 | ±14 | ±14 | ±14 | ±14 | ±14 | ±14 | ±14 | ±14 | ±14 | N/A |
| | Visit Type | InP | OP/HH ⁵ | InP | OP/HH ⁵ | InP | OP/HH ⁵ | InP | OP/HH ⁵ | InP | OP/HH ⁵ | InP | OP | OP | InP |
| Collect and re-issue Morning Glucose Level monitoring worksheet ¹⁵ | X | X | X | X | X | X | X | X | X | X | X | X | X | X | X |
| Assessment of morning glucose levels ¹⁶ | X | X | X | X | X | X | X | X | X | X | X | X | X | X | X |
| Dinner before controlled fasting challenge ¹⁷ | X | | X | | X | | X | | X | | X | | | | X |
| Cornstarch dose after dinner but before starting controlled fasting challenge ¹⁸ | X | | X | | X | | X | | X | | X | | | | X |
| Controlled fasting challenge ¹⁹ | X | | X | | X | | X | | X | | X | | | | X |
| Glucose and lactate (venous) sample (local laboratory [STAT sample]) ²⁰ | X | | X | | X | | X | | X | | X | | | X | X |

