¹ During the first year of Study 401GSDIA02, visits will occur approximately every 13 weeks.

² After the first year of Study 401GSDIA02, visits will occur approximately every 26 weeks.

³ The first visit for Study 401GSDIA02 may coincide with the Week 52/EOS/EW visit for Study 401GSDIA01. Assessments required for Study 401GSDIA02 that are the same as those performed during the Week 52/EOS/EW visit for Study 401GSDIA01 do not need to be repeated if written informed consent for Study 401GSDIA02 is obtained before the Week 52/EOS/EW assessments are performed for Study 401GSDIA01. Assessments may be performed on more than 1 day provided that all assessments are completed, and results are available within the 7-day window.

⁴ Visit will only be conducted if a subject has not yet entered the DTX401 DMP. Visit can be outpatient but should be in-clinic.

⁵ At Weeks 65, 91, 130, 182, and 234, every effort will be made to conduct an on-site assessment. However, under extenuating subject circumstances that, in the Investigator's opinion, make an on-site visit not feasible, and after all reasonable measures to enable the subject's onsite visit have been exhausted, a home healthcare visit and/or telemedicine assessment may be conducted. At these time points, the assessments in parentheses "(X)" will not be performed if the visit is changed to a home healthcare visit.

- ⁶ Any AEs that are ongoing at the completion of Study 401GSDIA01 will be considered medical history in Study 401GSDIA02.
- ⁷ Assessments to be performed prior to the controlled fasting challenge.
- ⁸ A blood sample for measurement of lipid levels will be collected on the morning of hospital admission for each controlled fasting challenge at approximately the same time starting at Day 0 (Study 401GSDIA01). The sample should be collected at least 2 to 4 hours after the subject's last meal.
- ⁹ If possible, a blood sample for measurement of cortisol, ACTH, free fatty acids, glucagon, insulin, C-peptide, growth hormone, IGFBP1, alanine and ketone levels (3-hydroxy butyrate) will be collected at the beginning and end of the controlled fasting challenge, or more frequently at the investigator's discretion.
- ¹⁰ A targeted physical examination will occur if a subject is not completing an end of study visit and a complete physical examination will occur if a subject is having an end of study visit.

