10.3.1. Adverse Events

All AEs will be recorded from the time the subject signs the ICF and up to the end of study (EOS; Week 312 or Week 208 if the last subject enrolls into the DMP) or Early Withdrawal visit. Serious AEs will be recorded for up to 30 days after the EOS or Early Withdrawal visit. The determination, evaluation, reporting, and follow up of AEs will be performed as outlined in [Section 11](#). At each visit, subjects will be asked about any new or ongoing AEs since the previous visit. Assessments of AEs will occur at each study visit.

Clinically significant changes from Visit 1 will be recorded as AEs or SAEs, if appropriate.

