10.3.6. Hypoglycemic Events

At each visit, the study site will instruct subjects on proper glucose monitoring at home, the signs and symptoms of hypoglycemia, and supplemental glucose treatment if needed. During each visit, the study site will record the number of symptomatic hypoglycemia events in the eCRF.

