12.4.2. Hypoglycemic Events

The number of symptomatic hypoglycemic events occurring during the study reported by the subjects will be summarized. Details of the symptomatic hypoglycemic events will be provided in a listing.

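### Symptomatic hypoglycemic events are counted per visit with no stated recall period, although visit spacing goes from about 13 to about 26 weeks after Week 104

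*SAP*

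**What the plan says.** SAP 6.9.6 gives the planned summary: "The number of subjects reporting symptomatic hypoglycemic events as captured in eCRF and number of events will be summarized by visit". It pools Study 401GSDIA01 and Study 401GSDIA02 and adds a listing of event details. It names no recall period, no subject-time and no rate.

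On collection, Protocol 10.3.6 says: "During each visit, the study site will record the number of symptomatic hypoglycemia events in the eCRF". Protocol Table 1 schedules the row "Assessment of symptomatic hypoglycemic events" at every visit. On analysis, Protocol 12.4.2 says: "The number of symptomatic hypoglycemic events occurring during the study reported by the subjects will be summarized". The amendment history for Version 2.0 describes the same intent: "Text was added to clarify that the reporting period for hypoglycemic events is throughout the study".

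On timing, the footnotes to Protocol Table 1 say "During the first year of Study 401GSDIA02, visits will occur approximately every 13 weeks" and "After the first year of Study 401GSDIA02, visits will occur approximately every 26 weeks". Week 130 is therefore the first visit that follows a 26-week gap.

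An explicit look-back to the previous visit is given only for adverse events, in Protocol 10.3.1: "At each visit, subjects will be asked about any new or ongoing AEs since the previous visit".

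**The concern.** A count taken at every visit can cover all events during the study only if each count runs back to the previous visit. That makes the since-previous-visit reading the natural one, although it is not written down for this measure. If it is correct, the counts at Weeks 65 to 104 each cover about 13 weeks and those from Week 130 about 26 weeks, and the planned table puts them side by side with nothing to show the difference in exposure.

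A reader could then take a schedule-driven rise at Week 130 for more hypoglycemia, or miss a real improvement at the same point. The study's primary objective is long-term safety, so the time course of this table is what a reader would look at. Visits within each block remain nominally comparable; the problem lies at the join. The documents do not give the visit spacing of Study 401GSDIA01, so nothing is claimed about that part of the table.

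**Working it through.** The documents give no event rate or expected count, so there is no figure of the plan's own to reproduce.

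**Inputs from the documents.** Scheduled visits at Weeks 91, 104 and 130 with windows of ±14 days (Protocol Table 1); 12 subjects in four cohorts of 3 (Protocol Synopsis); tables by cohort, Cohorts 2-4 combined and overall (SAP 6.1).

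**Assumptions.** Counts run from visit to visit. Rates of 1, 2 and 4 events per subject-year are illustrative. All 12 subjects continue and are seen at both visits. The year has 52 weeks, and events are Poisson.

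**Step 1, nominal ratio.** (130 − 104)/(104 − 91) = 26/13 = 2.0. At a constant rate this does not depend on the rate or on the number of subjects.

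**Step 2, effect of visit windows on one subject.**
- Smallest: Week 91 two weeks early, Week 104 two weeks late, Week 130 two weeks early gives (26 − 4)/(13 + 4) = 22/17 = 1.29.
- Largest: the opposite shifts give (26 + 4)/(13 − 4) = 30/9 = 3.33.
- If events are recorded at an unscheduled visit between Weeks 104 and 130 and not carried forward, the Week 130 count covers less time and the ratio falls further.

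**Step 3, expected events and sampling error.** Expected events = subjects × rate × interval/52. The standard deviation (SD) of the difference between two independent Poisson counts is the square root of their sum. For example, overall at rate 2: 12 × 2 × 13/52 = 6 and 12 × 2 × 26/52 = 12; step 6, SD √18 = 4.2, so 1.4 SD.

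| Column (subjects) | Rate 1 | Rate 2 | Rate 4 |
|---|---|---|---|
| One cohort (3) | 0.75 → 1.5 (0.5 SD) | 1.5 → 3 (0.7 SD) | 3 → 6 (1.0 SD) |
| Cohorts 2-4 (9) | 2.25 → 4.5 (0.9 SD) | 4.5 → 9 (1.2 SD) | 9 → 18 (1.7 SD) |
| Overall (12) | 3 → 6 (1.0 SD) | 6 → 12 (1.4 SD) | 12 → 24 (2.0 SD) |

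**Step 4, subjects with at least one event.** The proportion is 1 − exp(−rate × interval/52). It goes from 22% to 39%, from 39% to 63% and from 63% to 86% at rates 1, 2 and 4, which is 1.78-, 1.61- and 1.37-fold. The subject count is distorted less than the event count.

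**Step 5, a true halving after Week 104.** Overall, 12 × (rate/2) × 26/52 = 3, 6 or 12 events, the same as the Week 104 values. The improvement would not show.

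**Step 6, missed visits.** If Week 156 is missed, the Week 182 count covers 182 − 130 = 52 weeks, twice the nominal interval.

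**Step 7, with subject-time.** Overall at rate 2: 6 events/3.0 subject-years = 2.0 at Week 104 and 12/6.0 = 2.0 at Week 130. The step disappears.

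**The case against.** The strongest objection is that the period is set by the eCRF, which is not among the documents. Fixed look-backs are used for related measures: 4 weeks for CGM-defined events (SAP 6.8.4), and 7 days in the PGI-S question on low blood sugar (SAP Appendix 6). If the symptomatic count also has one, no step arises. This stands, and it is why the point is conditional. It does not remove the need to state the period.

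A reader might infer that this table will show hypoglycemia doubling at Week 130. The documents do not support that. The doubling is a nominal expectation under an unstated recall period, visit windows and unscheduled visits alter it, and with at most 12 subjects it would often be lost in sampling variation. At the assumed rates only the highest, in the overall column, reaches 2 SD, and variation between subjects would make it harder still to see.

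Other outputs help in part:
- Event details are listed.
- The CGM summary covers a fixed 4 weeks, but it counts sensor events and not subject-reported ones.
- SAP 6.9.1 tabulates TEAEs by year since dosing, which visit spacing does not affect. Hypoglycemia appears there only if it is reported as an AE, and Protocol 10.3.7 keeps clinically significant GSDIa-associated safety findings out of AE reporting unless they are judged more severe than expected.

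None of these gives the rate of subject-reported symptomatic events over time.

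**Conclusion.** The point holds as a minor one. The plan tabulates event counts by visit across a change in visit spacing and does not say what period each count covers. If counts run from the previous visit, which the protocol implies, a constant rate gives a nominal 2-fold step in expected events between Week 104 and Week 130, with 1.29 to 3.33 as the range for one subject within the visit windows. At the assumed rates the overall step is about 1 to 2 Poisson SDs; in a single cohort it is at most 1.

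A reader might also infer that the primary safety endpoint is affected. It is not: that endpoint is the incidence of AEs and SAEs, and symptomatic hypoglycemic events are a safety assessment outside the endpoints named in Protocol 12.1.1 to 12.1.3. No hypothesis is tested, so no error rate is at stake. What is at risk is a misread time trend in one descriptive table.

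**What to change.** State the eCRF recall period in SAP 6.9.6. If it is a fixed look-back, say so and keep the by-visit table as planned.

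If it is since the previous visit, keep the raw counts and add events per subject-time: total events divided by total time since each subject's previous attended visit. Show the number of subjects and the subject-time by cohort, for Cohorts 2-4 combined and overall. Using the previous attended visit also deals with missed visits. Three rules complete it:
- Add events and time from unscheduled visits to the next scheduled visit.
- Where the Week 52/EOS/EW visit of Study 401GSDIA01 and Visit 1 of Study 401GSDIA02 coincide, count them once. Where they do not, start the Visit 1 interval at the subject's last visit in Study 401GSDIA01.
- Show baseline as a raw count only, unless its look-back period is known.

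The cost is one check of the eCRF, a short addition to SAP 6.9.6, one derived variable from visit dates already used for study day (SAP 4.2), and slightly larger tables. No new data are needed.
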